Statistical Methods	
Analysis Populations
 
The following analysis sets will be defined for this study.
 
The safety analysis set comprises all enrolled patients who receive any quantity of study treatment, regardless of eligibility. The safety evaluation will be performed based on the first dose of study treatment a patient receives, regardless of the patient's cohort assignment. The safety analysis set will be used for all dosing/exposure and safety analyses.

[figure not shown]
	
The DLT-evaluable population (safety lead-in only) comprises patients who have either completed the DLT-observation period (1 cycle, 28 days) and received at least 75% of planned doses of the tarloxotinib and sotorasib combination in cycle 1 or have discontinued study treatment or study participation before completing cycle 1 due to a DLT.
 
The intention to treat (ITT) analysis set comprises all patients in the safety analysis set eligible for study inclusion and who meet the inclusion criteria for dose expansion, including eligible safety lead-in patients treated at the combination RP2D. This analysis set will be used for all efficacy analyses.
 
Safety lead-in
 
A minimum of 6 patients and as many as 18 patients will be enrolled in a safety lead-in cohort to evaluate the safety of the combination of tarloxotinib and sotorasib. Sotorasib will be held at a fixed dose of 960 mg QD (the approved dose) while the starting dose of tarloxotinib will be the monotherapy RP2D equal to 150mg/m² QW (dose level 1 [DL1]). Following a 3+3 algorithm, an initial 3 patients will be enrolled at DL1. If 0 or 1 of 3 patients experience a DLT, an additional 3 patients will be enrolled to DL1. DL1 will be declared the combination RP2D (RP2D_c) if at most 1 of 6 patients treated at DL1 experience a DLT. Alternatively, if there are 2 or more DLTs observed at DL1, 3 patients will be enrolled at DL -1 and the 3+3 rules repeated for safety evaluation. The RP2D_c will be the highest DL at which at most 1 patient of 6 experiences a DLT. If DL -2 is considered too toxic, additional dose levels below DL -2 may be evaluated for safety.
 
Dose expansion
 
Once the tarloxotinib RP2D_c is reached, an expansion cohort of up to 12 patients will be enrolled to evaluate the safety of the combination of tarloxotinib and sotorasib. Eligible safety lead-in patients treated at the RP2D_c will be included in the expansion cohort.

--	---

TABLE OF CONTENTS

1	SCHEMA	6

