4 SUBJECT SELECTION

4.1 INCLUSION CRITERIA

Patients eligible for study participation must meet all the following criteria:

- 1) Histologically confirmed diagnosis of squamous or non-squamous NSCLC with *KRAS* G12C mutation
- 2) Unresectable or metastatic disease
- 3) No available treatment with curative intent
- 4) Must have previously received treatment with at a platinum-containing chemotherapy regimen. Additional prior therapies for metastatic *KRAS* G12C mutated NSCLC are also permitted.
- 5) Must have previously received at least one month trial of sotorasib or a therapy targeting *KRAS* G12C mutation with documented progression. If sotorasib dose from prior therapy was reduced for toxicity, patients that meet the above criteria are expected to receive study treatment at the reduced dose.
- 6) Must have measurable or evaluable disease as defined by RECIST 1.1
- 7) Age >18 years

- 8) Life expectancy of at least 3 months
- 9) Recovery from adverse effect of prior therapy at the time of enrollment
- 10) Eastern Cooperative Oncology Group (ECOG) performance status of 0 or 1
- 11) Laboratory values within the screening period:
 - a) Absolute neutrophile count > 1000/mm³
 - b) Platelet count > 100,000 /mm³
 - c) Hemoglobin > 8 in the absence of transfusions for at least 2 weeks
 - d) Total bilirubin < 1.5 x upper limit of normal (or < 3 x ULN if associated with liver metastases or Gilbert's disease)
 - e) Aspartate transaminase (AST) or alanine transaminase (ALT) < 3 x ULN (or < 5x ULN if associated with liver metastases)
 - f) Creatinine clearance (CrCl) > 60 mL/min calculated by CKD-EPI or MDRD
- 12) Women of child-bearing potential agrees to use contraception while participating in the study and for a period of 6 months following termination of study treatment
- 13) Completed informed consent process
- 14) Willing to comply with clinical trial instructions and requirements.

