11 STATISTICAL CONSIDERATIONS

11.1 STUDY DESIGN

Study CTO # 103048 is a potentially multicenter, non-randomized, single cohort phase IB trial evaluating the safety and efficacy of tarloxotinib in combination with sotorasib in NSCLC patients with KRAS G12C mutation who have progressed on any small molecule KRAS G12C inhibitor.

Safety lead-in

A minimum of 6 patients and as many as 18 patients will be enrolled in a safety lead-in cohort to evaluate the safety of the combination of tarloxotinib and sotorasib. Sotorasib will be held at a fixed dose of 960 mg QD (the approved dose) while the starting dose of tarloxotinib will be the monotherapy RP2D equal to 150mg/m² QW (dose level 1 [DL1]). Following a 3+3 algorithm, an initial 3 patients will be enrolled at DL1. If 0 or 1 of 3 patients experience a DLT, an additional 3 patients will be enrolled to DL1. DL1 will be declared the combination RP2D (RP2D_c) if at most 1 of 6 patients treated at DL1 experience a DLT. Alternatively, if there are 2 or more DLTs observed at DL1, 3 patients will be enrolled at DL -1 and the 3+3 rules repeated for safety evaluation. The RP2D_c will be the highest DL at which at most 1 patient of 6 experiences a DLT. If DL -2 is considered too toxic, additional dose levels below DL -2 to be determined may be considered for safety.

Dose expansion

Once the tarloxotinib RP2D_c is reached, an expansion cohort of up to 12 patients will be enrolled to evaluate the safety of the combination of tarloxotinib and sotorasib. Eligible safety lead-in patients treated at the RP2D_c will be included in the expansion cohort.

The combination of tarloxotinib and sotorasib will not be considered promising if there is weak evidence the true objective response rate (ORR) exceeds 20%. Specifically, the trial will be declared negative if $\text{Prob}(\text{true ORR} > 20\% | \text{observed no. of responses}) < 20\%$, equivalent to observing at most 1 response in 12 patients. We assume the true ORR follows a beta (0.5, 0.5) prior distribution and, conditional on the true ORR, the number of responses follows a binomial distribution. If at least 2 responses in 12 patients are observed, the combination may be considered promising. Given 1 response in 12 patients, the probability the true ORR exceeds 20% is approximately 16%. Given 2 responses in 12 patients, the probability the true ORR exceeds 20% is approximately 42%.

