11.1.2 POPULATIONS FOR ANALYSES

The following analysis sets will be defined for this study.

The **safety analysis set** comprises all enrolled patients who receive any quantity of study treatment, regardless of eligibility. The safety evaluation will be performed based on the first dose of study treatment a patient receives, regardless of the patient's cohort assignment. The safety analysis set will be used for all dosing/exposure and safety analyses.

The **DLT-evaluable population (safety lead-in only)** comprises patients who have either completed the DLT-observation period (1 cycle, 28 days) and received at least 75% of planned doses of the tarloxotinib and sotorasib combination in cycle 1 or have discontinued study treatment or study participation before completing cycle 1 due to a DLT.

The **intention to treat (ITT) analysis set** comprises all patients in the safety analysis set eligible for study inclusion and who meet the inclusion criteria for dose expansion, including eligible safety lead-in patients treated at the RP2D_c. This analysis set will be used for all efficacy analyses.

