11.2.2 ANALYSIS OF THE PRIMARY EFFICACY ENDPOINT(S)

Objective response rate (ORR), defined as the proportion of patients who achieve a best overall response of CR or PR, is the primary efficacy endpoint. Tumor response will be measured and recorded using RECIST 1.1 guidelines (Eisenhauer et al. 2009). All lesions should be radiologically evaluated using the same method used for baseline evaluation. Any CR or PR will require confirmation at least 4 weeks following initial response observation. Objective response rate will be summarized for the ITT population using frequencies and proportions. A 95% CI for the ORR will be constructed using exact binomial (Clopper-Pearson) methods.

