11.3 INTERIM ANALYSES

Safety lead-in

Safety and tolerability data will be reviewed on a cohort-by-cohort basis during safety lead-in to determine if an additional cohort of patients should be enrolled at the current DL, if de-escalation is warranted, or if the protocol should be amended to evaluate additional intermediate or lower DLs. The final determination of the RP2D_c will be based on the totality of data including, but not limited to, safety and early signs of anti-tumor activity.

Dose expansion

Interim futility analysis. Given the limited sample size, there will be no futility interim analysis in the dose expansion cohort.

Continuous safety monitoring. Bayesian toxicity monitoring will be used to perform continuous safety monitoring of patients enrolled in the expansion cohort. Specifically, patients enrolled in the expansion cohort will be monitored for incidence of DLT-equivalent (DLT-E) events, defined as any safety event that would have qualified as a DLT had that patient been enrolled in the safety lead-in portion of the study. We assume the true DLT-E rate follows a beta (0.5, 0.5) prior distribution and, conditional on the true DLT-E rate, the number of patients who experience a DLT-E follows a binomial distribution. If $\text{Prob}(\text{DLT-E rate} > 33\% | \text{observed no. DLT-Es}) > 50\%$, trial enrollment will be paused. (Note: The observed number of DLT-Es will include DLTs from eligible safety lead-in patients treated at the RP2D_c who are included in the expansion cohort. Bayesian toxicity monitoring parameters were selected to calibrate with the 3+3 de-escalation rules used in the safety lead-in.) If the trial is paused, the safety review committee will review the totality of the safety data and determine whether to continue patient enrollment at the current RP2D_c, introduce intermediate or lower dose levels for evaluation, or close the trial to accrual and declare the combination of tarloxitinib and sotorasib too toxic. This monitoring rule has a 13% and 95% probability of pausing if the true DLT-E rate is 10% or 50%, respectively. The table below specifies safety monitoring thresholds.

Bayesian toxicity monitoring boundaries		
No. of patients	No. of DLT-Es to pause study	Observed DLT-E rate
6	≥2	≥0.33
7-9	≥3	≥0.33
10-11	≥4	≥0.36
12 – expansion cohort fully accrued		

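### The ORR denominator has no measurable-lesion condition, so evaluable-only patients, if any enrol, modestly raise the chance of a wrong negative call

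*Combined protocol and SAP*

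**What the plan says.** - **Eligibility.** The Synopsis and section 4.1, item 6, both state: "Must have measurable or evaluable disease as defined by RECIST 1.1". Evaluable disease is an alternative to measurable disease.
- **Efficacy set.** Section 11.1.2 (and the Synopsis) says the ITT set "comprises all patients in the safety analysis set eligible for study inclusion and who meet the inclusion criteria for dose expansion", and uses it for every efficacy analysis. Only one inclusion list is printed, so the reference to criteria for dose expansion does not screen out evaluable-only patients.
- **Carry-over.** The Synopsis and section 11.1 add: "Eligible safety lead-in patients treated at the RP2D_c will be included in the expansion cohort".
- **Endpoint.** ORR is a primary objective (section 2.1). Section 11.2.2 says "Tumor response will be measured and recorded using RECIST 1.1 guidelines" and "Objective response rate will be summarized for the ITT population using frequencies and proportions". A responder is a patient whose best overall response is a confirmed CR or PR.
- **Decision rule.** Under section 11.1, "an expansion cohort of up to 12 patients will be enrolled". The trial is declared negative if the posterior probability that the ORR exceeds 20% is below 20%, which the section describes as "equivalent to observing at most 1 response in 12 patients".

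**The concern.** Eligibility distinguishes two kinds of disease, but the efficacy analysis applies one responder definition to both. PR under RECIST 1.1 is a change in the sum of target-lesion diameters. A patient without a measurable lesion has no such sum and can count as a responder only through CR.

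The negative call separates 1 response from 2 in a cohort of at most 12. Each evaluable-only patient takes a place in the denominator with little chance of adding to the numerator. The expected ORR then falls, and a negative call becomes more likely, because of case mix and not drug activity. The harm lies at true ORRs above 20%, where a negative call would be wrong.

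**Working it through.** **Inputs from the documents (section 11.1).** n = 12 (a maximum), prior Beta(0.5, 0.5), benchmark ORR 20%, negative if the posterior probability is below 20%.

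**Assumptions (not in the documents).** m = number of evaluable-only patients among the 12, taken as 0, 1 or 2; p = true ORR in measurable patients, taken as 25% or 30%; q = CR rate in evaluable-only patients, taken as 0 or 5%.

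**Step 1: the plan's own figures.** With x responses the posterior is Beta(0.5 + x, 12.5 − x).
- x = 1: Beta(1.5, 11.5), P(ORR > 20%) = 0.155; the plan states about 16%.
- x = 2: Beta(2.5, 10.5), P(ORR > 20%) = 0.415; the plan states about 42%.

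Both reproduce. Since 0.155 < 0.20 < 0.415, so does the boundary of at most 1 in 12.

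**Step 2: probability of a negative call.** Responses = Bin(12 − m, p) + Bin(m, q), and the call is negative if the sum is at most 1.

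With q = 0 this is (1 − p)^(12−m) + (12 − m)·p·(1 − p)^(11−m). At p = 25%:
- m = 0: 0.75^12 + 12 × 0.25 × 0.75^11 = 0.0317 + 0.1267 = 0.158
- m = 1: 0.75^11 + 11 × 0.25 × 0.75^10 = 0.0422 + 0.1549 = 0.197
- m = 2: 0.75^10 + 10 × 0.25 × 0.75^9 = 0.0563 + 0.1877 = 0.244

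With q = 5% and m = 1, the single-response term is multiplied by 0.95: 0.0422 + 0.1549 × 0.95 = 0.189. The other cells follow in the same way.

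| True ORR p | CR rate q | m = 0 | m = 1 | m = 2 |
|---|---|---|---|---|
| 25% | 0 | 15.8% | 19.7% | 24.4% |
| 25% | 5% | 15.8% | 18.9% | 22.6% |
| 30% | 0 | 8.5% | 11.3% | 14.9% |
| 30% | 5% | 8.5% | 10.8% | 13.7% |

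**Step 3: expected ORR.** With q = 0 it is (12 − m)p/12. For m = 0, 1, 2 this gives 25.0, 22.9, 20.8% at p = 25%, and 30.0, 27.5, 25.0% at p = 30%.

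**Step 4: dropping these patients after the fact.** With 1 response and n patients the posterior is Beta(1.5, n − 0.5). P(ORR > 20%) is 0.155 at n = 12, 0.188 at n = 11 and 0.226 at n = 10. At n = 10 the same single response is no longer negative, so the denominator has to be settled before data are seen.

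**The case against.** **The CR-only premise is not printed in the documents.** True: the plan does not define PR or target lesions. But it adopts RECIST 1.1 by name for eligibility, endpoint and analysis, so that standard's definition of PR governs the analysis. Nor does the result need a zero response rate: the 5% rows show the same direction with a slightly smaller effect.

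**The effect is hypothetical and small.** This stands as a limit on size. The documents give no expected m. One such patient adds 3.9 points at a true ORR of 25% and 2.8 at 30% (3.1 and 2.3 with a 5% CR rate). The plan's own exact 95% interval for 2 of 12 runs from 0.02 to 0.48, so ORR will be imprecise in any case.

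**Counting every eligible treated patient is a legitimate, conservative choice.** This is fair, and section 11.1 describes the expansion as evaluating safety, for which evaluable-only patients are fully informative. But ORR is also a primary objective with a formal negative rule, and the 20% benchmark makes no stated allowance for patients who cannot score a PR. A lighter option is to keep the denominator and pre-specify a descriptive ORR in measurable patients. That would show the dilution but leave it in the decision.

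**Stronger readings that the documents do not support.**
- A reader might infer that the plan leaves open how an evaluable-only patient is counted. It does not: sections 11.1.2 and 11.2.2 together put the patient in the denominator, as a non-responder unless a CR or PR is confirmed.
- A reader might infer harm at true ORRs of 20% or below. The probability of a negative call rises there too, but that call is not an error against the plan's benchmark.
- A reader might infer that toxicity monitoring is already weakened. It is not: under the current text an eligible evaluable-only lead-in patient treated at the RP2D_c stays in the monitored cohort.

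**Conclusion.** The point holds as a conditional gap in the efficacy population. Criterion 6 admits evaluable-only patients, nothing removes them from the ORR denominator, and the negative call turns on a single response. The calculations in section 11.1 are correct.

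At true ORRs of 25 to 30%, one such patient among 12 raises the probability of a wrong negative call by about 2 to 4 points, and two raise it by about 5 to 9. These ranges rest on the assumed m of 1 or 2 and a CR rate of 0 to 5%. If no evaluable-only patient enters the set, nothing changes. The gap should be closed because the change is small and the denominator should not be open to choice once responses are known, but it does not undermine the design.

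**What to change.** 1. Require at least one RECIST 1.1 measurable lesion at baseline for every patient counted in the 12-patient efficacy cohort, including carried-over lead-in patients. State this with criterion 6 (Synopsis and section 4.1), in the ITT definition (Synopsis and section 11.1.2) and in the carry-over sentences (Synopsis and section 11.1). Evaluable-only patients may still enter the safety lead-in. The n = 12 rule and the 16% and 42% figures then stand unchanged.
2. Add one sentence to section 11.3 keeping all eligible lead-in patients treated at the RP2D_c in DLT-E monitoring, whether or not they count for efficacy. Step 1 makes this necessary, because section 11.3 counts lead-in DLTs only for patients "who are included in the expansion cohort". Without it, removing an evaluable-only patient who had a DLT could turn 3 DLT-Es in 9 (Beta(3.5, 6.5), P(rate > 33%) = 52.5%, pause) into 2 in 8 (Beta(2.5, 6.5), 33.0%, no pause).
3. Say whether the limit of 12 is the efficacy count or the safety count. If the safety count can exceed 12, extend the monitoring table, which stops at 11, by the plan's own 50% criterion: 4 of 12 gives 52.4%, 4 of 13 gives 44.6% and 5 of 13 gives 67.2%, so the thresholds are 4 at 12 and 5 at 13.
4. Do not apply the efficacy rule to a reduced denominator after the fact.

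**Cost.** A few sentences. The accrual pool for expansion narrows by an amount that the documents do not let us estimate, in a trial that recruits mainly from one centre's clinics (section 5.1). An evaluable-only lead-in patient may need a replacement in the efficacy count.

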4.2 EXCLUSION CRITERIA

Patients eligible for study participation CANNOT meet any of the following criteria:

- 1) Active, untreated brain metastases. Patients are eligible if brain metastases are previously treated and asymptomatic. Patients must be neurologically stable and on a stable or tapering dose of corticosteroids for at least 2 weeks prior to C1D1.
- 2) History of intestinal disease or major gastric surgery likely to alter absorption of study treatment or inability to swallow pills
- 3) Congestive heart failure > NYHA Class 3
- 4) QTc > 480 milliseconds or family history of Long QT syndrome
- 5) Ongoing need for a medication with a known risk of Torsades de Pointes that cannot be switched to alternative treatment prior to study entry.
- 6) Pregnancy or breast feeding
- 7) Has known activating non-KRAS G12C oncogene-driver mutations, including but not limited to: ALK, ROS1, RET, BRAF, NTRK1/2/3, MET, EGFR.
- 8) Previously have received anti-EGFR or anti-HER2 TKIs
- 9) Previously have received anti-EGFR or anti-HER2 monoclonal antibodies
- 10) Clinically active or symptomatic interstitial lung disease

- 11) Known concurrently malignancy that is expected to require active treatment within 2 years or may interfere with the interpretation of the efficacy and safety outcomes of this study.
- 12) Infection requiring systemic treatment within 7 days prior to cycle 1 day 1.
- 13) Patients with known hypersensitivity to either tarloxitinib, sotorasib, or any of the ingredients.

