7.2 SOTORASIB

7.2.1 Description

Sotorasib is an inhibitor of the RAS GTPase family. The molecular formula is C₃₀H₃₀F₂N₆O₃, and the molecular weight is 560.6 g/mol. The chemical name of sotorasib is 6-fluoro-7-(2-fluoro-6-hydroxyphenyl)-(1M)-1-[4-methyl-2-(propan-2-yl)pyridin-3-yl]-4-[(2S)-2-methyl-4-(prop-2-enoyl)piperazin-1-yl]pyrido[2,3-d]pyrimidin-2(1H)-one.

Sotorasib has pKa values of 8.06 and 4.56. The solubility of sotorasib in the aqueous media decreases over the range pH 1.2 to 6.8 from 1.3 mg/mL to 0.03 mg/mL.

Sotorasib is supplied as film-coated tablets for oral use containing 120 mg. Inactive ingredients in the tablet core are microcrystalline cellulose, lactose monohydrate, croscarmellose sodium,

and magnesium stearate. The film coating material consists of polyvinyl alcohol, titanium dioxide, polyethylene glycol, talc, and iron oxide yellow.

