7.2.8 Dose Modifications for Adverse Reactions

Dose level -1	480mg once daily
Dose level -2	240mg once daily

Sotorasib should be discontinued if further dose reduction is indicated below 240mg once daily.

Adverse reaction	Dosage modification
Grade 2 AST or ALT elevation with symptoms Grade 3-4 AST or ALT	
 Hold sotorasib dosing until recovery to Grade 1 or resolution Resume sotorasib dosing at the next lower dose level
AST or ALT > 3 x ULN with total bilirubin > 2 x ULN in the absence of alternative causes	
 Permanently discontinue sotorasib
Interstitial Lung Disease (ILD) or pneumonitis, any grade	
 Hold sotorasib dosing if either is suspected Permanently discontinue sotorasib dosing if either is confirmed
Grade 3 nausea or Grade 3-4 vomiting despite appropriate supportive care (including anti-emetic therapy)	
 Hold sotorasib dosing until recovery to Grade 1 or resolution Resume sotorasib dosing at the next lower dose level

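### A patient who recovered from ILD or serious liver injury on earlier sotorasib is not barred from re-exposure, although either event on study would end sotorasib permanently (minor safety gap)

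*Combined protocol and SAP*

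**What the plan says.** **Stopping rules (7.2.8).** If ILD or pneumonitis of any grade is suspected, sotorasib is held; the next instruction is "Permanently discontinue sotorasib dosing if either is confirmed". Sotorasib is also stopped permanently for "AST or ALT > 3 x ULN with total bilirubin > 2 x ULN in the absence of alternative causes".

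**Entry rules (4.1 and 4.2, repeated in the synopsis).**
- Exclusion 10: "Clinically active or symptomatic interstitial lung disease".
- Inclusion 9: "Recovery from adverse effect of prior therapy at the time of enrollment".
- Inclusion 11 d and e: bilirubin below 1.5 x ULN (3 x with liver metastases or Gilbert's) and AST or ALT below 3 x ULN (5 x with liver metastases), measured in the screening period.
- Inclusion 5: "Must have previously received at least one month trial of sotorasib or a therapy targeting" KRAS G12C, with documented progression. Where earlier sotorasib was reduced for toxicity, patients "are expected to receive study treatment at the reduced dose".
- Exclusion 13: known hypersensitivity to either drug. It mentions neither lung nor liver injury.

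**The concern.** Because of inclusion 5, earlier sotorasib exposure will be common, and every enrolled patient takes sotorasib. The authors considered earlier sotorasib toxicity, since inclusion 5 carries a reduced dose forward. They wrote nothing for the more serious case, in which sotorasib had to be stopped.

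The protocol regards two events as serious enough to end sotorasib for good during the trial, yet the same events before the trial do not count against entry. The stake is patient safety: a possible second lung or liver injury from a drug already known to have been followed by the first. A lesser stake is dose finding. Under 6.2, a related toxicity that forces permanent discontinuation is a DLT, so a cycle 1 recurrence would count against the tarloxotinib dose level.

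**Working it through.** The plan gives no figure to reproduce. The main check compares texts; the arithmetic only bounds the size.

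**1. Each stopping event against each entry rule that might catch it**

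| Past event on sotorasib, now resolved | Excl. 10 | Incl. 9 | Incl. 11 | Incl. 5 | Excl. 13 |
|---|---|---|---|---|---|
| Confirmed ILD/pneumonitis | Passes: not active or symptomatic | Passes: recovered | Not relevant | Silent on stopping | Not named |
| AST/ALT and bilirubin event of 7.2.8 | Not relevant | Passes: recovered | Passes: current values | Silent on stopping | Not named |

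**2. A patient who meets the written criteria.** Sotorasib is stopped for pneumonitis; the patient recovers, receives another KRAS G12C inhibitor for at least a month, progresses on it, and has normal screening tests. Inclusion 4 permits additional prior therapies. Inclusion 5 and the 11.1 population (progression on any small-molecule KRAS G12C inhibitor) are both satisfied. No exclusion applies.

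**3. How many patients could be exposed.** By 11.1, if the starting level passes, its 6 lead-in patients count within the expansion's 12, so there are 6 + 6 = 12 unique patients. If all three listed levels take 6 patients each and the lowest passes, there are 18 + 6 = 24. (This ignores replacement of non-evaluable patients and any further lower levels.) Let p be the share of candidates with such a history. The documents do not give p; it is assumed here and may be near zero.

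P(at least one) = 1 − (1 − p)^n

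| p (assumed) | n = 12 | n = 24 |
|---|---|---|
| 0.1% | 1.2% | 2.4% |
| 0.5% | 5.8% | 11.3% |
| 1% | 11.4% | 21.4% |
| 2% | 21.5% | 38.4% |

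These are chances of enrolling such a patient, not of harm. With an assumed 25% recurrence, p = 1% and n = 12 give 1 − (1 − 0.0025)^12 ≈ 3%; p = 2% and n = 24 give 1 − (1 − 0.005)^24 ≈ 11%.

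**4. Effect on the 3+3 decision.** A level passes with at most 1 DLT in 6. Let q be the background DLT rate (assumed) and k the probability of recurrence in cycle 1.

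P(pass) = P(Bin(6, (1 − p)q + pk) ≤ 1)

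- q = 0.15, p = 0: 0.85^6 + 6 × 0.15 × 0.85^5 = 0.776.
- Worst case k = 1, q = 0.15: 0.767, 0.756 and 0.736 for p = 0.5%, 1% and 2%.
- p = 2%, k = 1, with q = 0.10, 0.15, 0.20, 0.25 and 0.30: P(pass) falls by 0.037, 0.041, 0.039, 0.035 and 0.030.

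So even with certain recurrence and the largest share considered, the loss is about 0.04. At p = 0.5% it is about 0.01.

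**The case against.** The strongest reply has four parts.

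- **Entry and stopping rules answer different questions.** The limit to active or symptomatic ILD, and the acceptance of recovered toxicity, may be deliberate. This stands as far as it goes. A reader might infer that the protocol contradicts itself or breaches 7.2.8, but that section governs reactions on study, so the documents show only a mismatch.
- **The group is nearly closed off.** The design describes patients who progressed on a KRAS G12C inhibitor, so someone who stopped sotorasib for toxicity usually needs a second inhibitor and progression on it. This stands, and it is why the point is minor. One might read inclusion 5 alone as admitting any patient who stopped sotorasib for toxicity and progressed later, off treatment. That fits poorly with the population in 11.1, and the point does not rely on it.
- **Safeguards exist.** Medical history is taken at screening, source documents are audited before registration (section 5), and chemistry and oxygen saturation are checked at infusion visits. The visit checks act only after re-exposure. History and audit come before it, but no criterion in 4.1 or 4.2 lets them reject this patient. The audit procedures are in an Operations Manual that is not available here.
- **The frequencies are invented.** They are, and they are labelled as assumptions. They show a range and are not evidence that such patients will appear.

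Two further inferences go too far. First, inclusion 5 sets no floor and "Sotorasib is supplied as film-coated tablets for oral use containing 120 mg", so one might say that a patient earlier reduced to 120 mg would start in breach of a third permanent-stop rule. The wording is only "Sotorasib should be discontinued if further dose reduction is indicated below 240mg once daily", without permanence. The sole reduced levels defined are 480 and 240 mg, and 7.2.4 reports similar steady-state exposure from 180 to 960 mg, so 240 mg is not presented as a safety threshold comparable to lung or liver injury. (That range does not reach 120 mg, so it does not vouch for that dose either.) Second, not all entry criteria are confined to current status: exclusions 2, 4, 8, 9 and 13 look back. The gap is specific to these two events.

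**Conclusion.** The point holds as a minor patient-safety gap in eligibility. A recovered patient with confirmed ILD or pneumonitis, or the 7.2.8 liver event, on earlier sotorasib is not barred if progression later occurred on another KRAS G12C inhibitor. That conclusion comes from the text alone and needs no assumption.

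Its size cannot be estimated from the documents, and the number affected may be zero. A reader might infer that the recommended dose is at risk. The calculation does not support that: the worst case considered needs both a 2% share and certain recurrence in cycle 1. The case for change rests on avoiding a foreseeable re-exposure at almost no cost.

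**What to change.** Add one exclusion to 4.2 and the synopsis, using the protocol's own thresholds: *Confirmed ILD/pneumonitis of any grade, or "AST or ALT > 3 x ULN with total bilirubin > 2 x ULN in the absence of alternative causes", during earlier sotorasib treatment.* Have the eligibility audit check why earlier sotorasib was stopped. The wording is tied to the period of sotorasib treatment, which limits arguments about attribution after several therapies. It covers sotorasib only, because 7.2.8 does; the same event on another KRAS G12C inhibitor stays a matter of judgment.

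As an optional clarification, state in inclusion 5 that a carried-forward sotorasib dose must be 480 or 240 mg, the reduced levels that the protocol defines.

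The cost is possibly a few eligible patients, including anyone who had such an event, resumed sotorasib and then progressed on it. Some outside records will be needed, since 5.1.2 allows external referrals. Visits, tests and sample size do not change.
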